We will utilize a modified MIT schedule for this PMIT study with a randomized, double-blinded study based on our previous experience with peanut-allergic subjects. Active peanut allergy will be confirmed in all interventional subjects with open oral food challenge prior to entry into the study. Control subjects may be offered a confirmatory food challenge if the diagnosis is uncertain. We will enroll 80 children in the intervention group. The active subjects will be randomized into either a high dose group (final maintenance dose of peanut 3000mg, N=40) or a low dose group (final maintenance dose of peanut 300mg, N=40) (see Figure 1). Forty additional subjects will be followed as control subjects and will not receive any type of study protein. All subjects in the active group will undergo a one-day peanut desensitization protocol designed to enable the subject to tolerate a daily dose of peanut protein (modified rush phase) (Table 3). If the subject has a mild reaction to one of the doses, the next dose would be determined at the discretion of the investigator. The options open to the investigator are to administer the last previously tolerated dose, or wait an additional amount of time between doses, or repeat the current dose. Once this determination of the dosage amount is made, the desensitization process resumes as outlined. Upon completion of the modified rush phase to peanut, the subject is observed for a minimum of 2 hours. If there is no evidence of an allergic reaction the subject is discharged home.

If the subject requires treatment for symptoms during the initial escalation protocol with antihistamines on one occasion, then the rest of the protocol may be followed. If the subject requires more than one medication or multiple doses of antihistamines or requires other rescue medications, the initial desensitization phase should be stopped. If the subject has tolerated either the 3 mg or 6mg dose, the subject will be eligible to return on Day 2 to proceed with the build-up phase.

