After the first day of desensitization, subjects will return to the research unit to begin the build-up phase of the study. The subject will ingest 6 mg, or a lower amount based on the reaction to the modified rush phase. After the subject is observed for a minimum of 30 minutes for symptoms to the study protein ingestion, he or she will be discharged from the research unit and will continue to consume the study protein at home daily for a minimum of ten to fourteen days (+7 days). The family receives the study protein doses as a powder that they give to the child each day by sprinkling it on a previously tolerated food (e.g., applesauce). Subsequently, subjects will return to the clinical research unit every ten to fourteen days to monitor their adherence to the dosage administration and increase the dose to the next escalation amount (see Table 4). The subject's response to the new dose escalation amount will be monitored for a minimum of 30 minutes after dose administration. Vital signs are performed prior to the dose administration, prior to the completion of the observation period before discharge, and anytime symptoms occur. If attempts at blood pressure measurement have been very disturbing and traumatic to a young child, the study team will rely on observation, heart rate and respiratory rate and the physical assessment to determine the subject's response. If the study team feels that a longer observation time is warranted based on the prior dosing history of the subject or their current physical status, the subject will be observed for a longer period of time. If symptoms occur that do not require treatment, the subject will be observed until they resolve. If symptoms occur that require diphenhydramine or albuterol, the subject will be observed a minimum of 2 hours or until symptoms resolve. If symptoms occur that require epinephrine, the subject will be observed at least 4 hours or until symptoms resolve. If symptoms do not fully resolve after 6 hours or if new symptoms occur, the subject will be transferred to UNC Children's Hospital to be observed overnight. Subjects will then take that dose daily for a period of 10 to 14 days (+ 7 days) after which they will return to the clinical research unit to have the daily dose increased proportionately at each visit until the maximum daily dose of study protein (3000mg) is consumed. All active subjects will build up to 3000mg of study protein. To maintain blinding, the subjects randomized to the 300mg peanut dose will have additional placebo flour added to the study protein during buildup by unblinded study personnel. Laboratory studies will be done at the beginning of the study, when the subject reaches the 156 milligram dose, when the subject reaches the 749 milligram dose, and when the subject reaches the 3000mg dose, and annually thereafter until the end of the study. The laboratory studies will consist of blood tests to monitor the immune response to the peanut protein. Stool studies will be performed at the beginning of the study and the end of the study. Control subjects will have visits for medical history, physical exam, titrated skin prick testing and blood and stool laboratory studies associated with the study at entry and then yearly. This control group will be seen yearly over the length of the study.

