After completing the escalation schedule (*build up phase* to 3000 mg study protein), the subjects will continue to receive their maintenance dose of study protein daily for the next 36 months of the study (*maintenance phase*). Once subjects enter the maintenance phase, assessment of the primary endpoint will occur conditionally (i.e., upon achievement of defined immunological benchmarks), and/or at the chronological end of 36 months of maintenance. These two possible scenarios are discussed further below. After 12 months of maintenance, the subject will have the peanut-specific IgE measured. In the first conditional scenario, at any point after this measurement, if the peanut IgE is 15 kU/L or less, the skin test is 8mm or less, and there have been no severe symptoms following PMIT doses or accidental peanut exposure in the previous 6 months, at the discretion of the investigator, the subject will stop the daily dosing and have a DBPCFC the next day. This cohort of subjects will then stop the daily dosing for the next 4 weeks and then return for a 2nd DBPCFC to peanut to assess long term tolerance to peanut. If these food challenges are negative (i.e., successfully completed), they will be followed by an open peanut challenge. The open challenge will occur in a 1 to 2 hour window after the successful completion of the tolerance challenge, and the study will be completed for that participant if the open challenge is successful. If any of the challenges are positive or inconclusive (i.e., not successful), the participant will resume OIT dosing until the next 12 months, or at the end of the 36 month treatment period. In the second (i.e. chronological) scenario, all remaining subjects will be assessed for the primary endpoint once they have completed 36 months of maintenance treatment, regardless of their immunologic parameters and/or their performance in past challenges, if applicable. If either challenge at the end of 36 months are positive or inconclusive (i.e., not successful), the participant will be considered as having completed the study and will return to standard of care.

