Subjects who miss one to two days of the daily dose will continue at their current dose at home. The PI will determine where the next dose of study protein is given for those who miss three to four days of the daily dose based on the length of time on study, the daily dose amount, the subject's reaction history and the amount of time since the last reaction to a dose in order to assure safety with dosing. Those who miss more than four days will return to the clinical research unit for evaluation by the study team in order to determine the best course of action for the subject. Options open to the investigator include repeat desensitization, observed dosing at a dosing level previously tolerated by the subject, or a change from active subject to control subject. To monitor subjects for adherence, any accidental ingestion, any symptoms related to daily dosing and any unintended side-effects of daily dosing, the families will be asked to keep a simple daily diary to record the requested information. A copy of the daily diary is included on page 16 of the protocol.

We will monitor accidental reactions to peanuts in each subject during the PMIT trial. We will note any reaction that occurs in a subject after the ingestion of peanuts, and record the type of symptoms (i.e., skin, respiratory, gastrointestinal, or cardiovascular). Pilot data from our previous studies indicate that home dosing is safe, with infrequent reactions which are typically mild. These data have identified several risk factors for reactions, which include dosing on an empty stomach, fever/illness, and activity/exercise shortly after dosing. Families of subjects will be asked to administer the study protein with additional food such as at snack or meal times, and during illness to hold the study protein and contact study personnel for instruction.

Because of the extreme risk to subjects, those experiencing severe symptoms during dosing or challenges such as respiratory failure, hypotension or other symptoms requiring ICU care will be withdrawn from the study. Additionally any subjects who have had an accidental peanut ingestion and developed anaphylaxis with respiratory failure or hypotension during the time on PMIT will be dropped from the active portion of the study. Subjects that do not complete the study because of an accidental reaction to peanut will be followed in the control group.

Study Stopping Rules

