**Determining the Efficacy and Value of Immunotherapy on the
likelihood of peanut tolerance: The DEVIL Study**

Statistical Analysis Plan

NCT number NCT00932828

Document Date 04/08/2013

Sample size

No placebo-controlled studies have been published that evaluated the development of tolerance/SU after years of treatment with peanut OIT. Published data from our own uncontrolled pilot study in older children with long-standing disease suggest that SU developed in 12 of 24 (50%) peanut-allergic subjects completing high-dose OIT. (Vickery, et al. Sustained unresponsiveness to peanut in subjects who have completed peanut oral immunotherapy. *J Allergy Clin Immunol*. 2014 Feb;133(2):468-75. doi: 10.1016/j.jaci.2013.11.007). On the basis of preliminary data that were available to us at the time this study was conceived in 2008, and according to our hypothesis, we predicted before the study that 70% of low-dose subjects would develop SU, compared with the expected rate of spontaneous peanut allergy resolution of 20% as shown in multiple cohort studies. At a 2-sided significance level of .05, 15 subjects in each treatment arm would have at least 80% power to detect a 50% absolute average difference between the proportion of subjects in each arm passing the exit SU OFC and the 20% rate of spontaneous tolerance expected in untreated controls. On the basis of a prestudy assumption of 15% to 20% dropout, we enrolled 20 subjects per arm to ensure adequate power.

Practical considerations prevented a trial large enough to show definitive comparisons of high- and low-dose therapy directly. Twenty subjects in each arm would have 63% power to identify a 40% difference in SU acquisition between regimens. Even if underpowered to show a difference between low-dose and high-dose therapy, we reasoned a priori that a type II error in this setting may still be clinically meaningful so long as the proportion achieving SU in the low-dose group significantly exceeded 20%. This would be especially true if low-dose therapy offers other advantages (fewer visits, better safety profile, improved palatability, etc).

Randomization

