For the primary outcome analysis, subjects were considered a single intervention group on open label peanut OIT. For exploratory analyses, subjects were randomized 1:1 to be on either low dose OIT (300mg peanut protein) or high dose (3000mg peanut protein). Masking was achieved by the addition of oat flour to the low dose OIT in order to match the weight of the high dose OIT product. Patients, patient families, study coordinators and investigators were blinded to the dose allocation. Randomization was conducted by unblinded laboratory staff in the [name] lab using a block randomization scheme.

Statistical Analysis

We computed averages, variances, frequencies, proportions, and graphical displays for all variables and examined them to ensure parametric distributional assumptions were met. Nonparametric test statistics were used as appropriate. Baseline demographics and categorical peanut consumption outcomes were compared between E-OIT and controls using Fisher's exact test. Analyses were performed with GraphPad Prism 6 for Mac (La Jolla, CA) or Stata/SE 13.1 (College Station, TX). To achieve approximate normality and variance stabilization for longitudinal immune analyses, pslgE and pslgG4 were log-transformed, while for SPT raw data were employed. Models were fit separately for each group in R (www.r-project.org) for each outcome with functions of time using generalized estimating equations. Linear and quadratic,

and cubic models in time were considered, with the best fitting model selected for each group for each outcome selected using QIC. All hypothesis tests were two-sided, with $p < 0.05$ considered significant.

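### Some OIT children can be moved to the control group, and the SAP does not say in which group, or how, they are counted, so the OIT success rate can be modestly inflated

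*Protocol*

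**What the plan says.** The relevant protocol text is in the section on study design, dosage schedule and accidental reactions. It gives two routes from OIT to control.

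- **Accidental reaction.** "Subjects that do not complete the study because of an accidental reaction to peanut will be followed in the control group".
- **Missed doses.** When more than four days are missed, one of the investigator's options is "a change from active subject to control subject".

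The same section ties the endpoint to staying in treatment. A child may be challenged early, after 12 months of maintenance, if immunological criteria are met; a child who passes every challenge has finished the study. Otherwise, "all remaining subjects will be assessed for the primary endpoint once they have completed 36 months of maintenance treatment". For the control group, "Control subjects will have visits for medical history, physical exam, titrated skin prick testing and blood and stool laboratory studies" at entry and yearly. A food challenge is not on that list; controls may be offered one only to confirm an uncertain diagnosis.

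In the SAP, the Randomization section says that for the primary outcome "subjects were considered a single intervention group on open label peanut OIT". The Statistical Analysis section says that baseline demographics and "categorical peanut consumption outcomes were compared between E-OIT and controls", by Fisher's exact test. The Sample size section deals with non-completion only as an allowance: "On the basis of a prestudy assumption of 15% to 20% dropout, we enrolled 20 subjects per arm". Neither document names an intention-to-treat, per-protocol or as-treated set, assigns a moved child to a group, or says how a child without an exit challenge is scored.

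**The concern.** A child who stops OIT because of a reaction to accidental peanut exposure is a likely treatment failure. A child moved by either route has not passed the SU challenge, because passing everything would already have ended that child's participation. Some moved children may have an earlier failed challenge on record; others will have no exit result. If the analysis uses only children still in the OIT group, or only those with a 36-month challenge, likely failures leave the denominator and the reported SU rate rises.

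The missed-dose route is less clear in direction, since poor adherence is not the same as failure, but it is at the investigator's discretion. The controls are an additional untreated group outside the dose randomisation, so the comparison already lacks the protection of randomisation. The denominator rule should therefore be fixed in advance rather than chosen once results are known.

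**Working it through.** **Inputs**

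- SAP, Sample size: 70% SU predicted (for low dose), 20% expected without treatment, two-sided 0.05, 15 per arm for at least 80% power, 15% to 20% dropout, 20 enrolled per arm (40 pooled).
- Protocol, study design: 80 active children, and "Forty additional subjects will be followed as control subjects".
- Number of children moved: not given. A range is shown.
- Assumption: 70% is applied to the pooled OIT group, although the SAP predicts it for low dose.

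**The plan's own figure.** For 70% against 20%, the normal-approximation formula with pooled variance under the null and no continuity correction gives n = 14.3, so 15 per arm, with power 82.0% at n = 15. The SAP's figure reproduces, and this point does not depend on it.

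**Effect of one moved child.** If *s* children succeed among *N* treated and *m* without a pass are left out, the reported rate is s/(N − m) instead of s/N.

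- N = 40, m = 1: 28/40 = 70.0% becomes 28/39 = 71.8%, a rise of 1.8 points.
- N = 80, m = 1: 56/80 = 70.0% becomes 56/79 = 70.9%, a rise of 0.9 points.

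**Upper bound.** Assume that every dropout is a moved child, none of whom achieves SU, and that about 70% of those who stay succeed.

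| Dropout | Moved (of 40) | Remaining | Successes | Reported | Of all treated | Gap |
|---|---|---|---|---|---|---|
| 15% | 6 | 34 | 0.7 × 34 = 23.8, about 24 | 24/34 = 70.6% | 24/40 = 60.0% | 10.6 points |
| 20% | 8 | 32 | 0.7 × 32 = 22.4, about 22 | 22/32 = 68.8% | 22/40 = 55.0% | 13.8 points |

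**Does the conclusion change?** Take an illustrative control result of 8/40 (40 controls at 20%). Two-sided Fisher's exact test with all 40 OIT children kept gives p = 0.0005 for 24/40 and p = 0.0024 for 22/40. Both remain clearly significant.

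**Effect of the fix on power.** Scoring all dropouts as not achieving SU turns a planned 70% into 0.70 × 0.85 = 59.5% or 0.70 × 0.80 = 56.0%. Exact power of Fisher's test, 40 against 40 with controls at 20%, is 94.1% and 89.1% respectively.

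**The case against.** Several points on the other side stand.

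- **Follow-up may not mean analysis.** For the accidental-reaction route, being followed with the controls may mean only their yearly visits. The missed-dose wording is closer to a change of status. A reader might infer that moved children are added to the controls as failures, which would distort both groups. The documents do not say so, and it would need a literal reading of the missed-dose option alone.
- **The SAP does not define an exclusion.** A reader might take "subjects were considered a single intervention group on open label peanut OIT" to exclude children who have stopped. In context the sentence explains why the two doses are pooled. The gap is silence, not a stated exclusion.
- **The upper bound is not an estimate.** Treating the whole dropout allowance as reassignment is not supported. The only dropout breakdown in the documents is from the 28-child pilot (Preliminary Results): four left for personal reasons and one for eosinophilic esophagitis, with none attributed to accidental ingestion.
- **Borderline significance is not shown to be fragile.** Against an assumed 8/40, 17/40 gives p = 0.053 and 17/39 gives p = 0.031, so a reader might infer that one child decides the result. But the 8/40 is an assumed count on an outcome with no scheduled control challenge. The Sample size section sets SU against an expected 20%; against a fixed 20%, even 14/40 is already significant (exact binomial, two-sided, p = 0.027).

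None of this answers the core point. The protocol states the rules that move children, and neither document says how they are analysed.

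**Conclusion.** The concern holds as a gap in the analysis rules that should be closed. Followed as written, the protocol can take likely failures out of the OIT denominator, and nothing in the SAP prevents it. The supportable size is about 1.8 percentage points per omitted child with 40 treated and about 0.9 with 80. The 11 to 14 points is only a ceiling, reached if every dropout were a moved child without SU.

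The documents do not support saying that the trial's conclusion depends on this rule: at the planned rates it does not. What is at stake is the size of the reported SU rate, which families and clinicians would rely on. Confidence is moderate, because the number of moved children is unknown and the missed-dose route need not select failures.

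**What to change.** 1. In the protocol's study design section, state for both routes that control-group follow-up means the visit schedule only.
2. In the SAP, analyse every child who started OIT in the assigned dose arm and in the pooled OIT group, never as a control.
3. Count children without a passed exit SU challenge as not achieving SU.
4. Add a sensitivity analysis for children moved only because of missed doses, for example excluding them.
5. Report the number moved, with reason, by dose arm.

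The cost is a few sentences in the SAP and one clarification in the protocol. The reported SU rate may be lower, as shown in the working, but power remains adequate under the assumed 40 against 40 comparison. The rule settles the denominator; it does not remove confounding from the non-randomised controls.

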The following stopping rules will be used throughout the study. If a subject at any time point experiences a serious adverse event as described by the FDA or an unanticipated event of grade 3 or above as defined by the CTC III scale, the trial will be halted and the IRB and FDA will be consulted. If symptoms as noted above occur in 2 or more subjects, the study will be stopped and the situation reviewed. In addition, the study will not resume until the FDA has been notified and given the approval for the study to continue.

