Subjects will be dropped from the arm of the study ingesting daily maintenance dose of peanut protein if they are having moderate to severe clinical symptoms (GI, respiratory or skin) at home after taking the daily dose of peanut protein. Additionally, any subjects who have an accidental peanut ingestion and have anaphylaxis during the time on oral desensitization, will be dropped from the arm of the study ingesting daily maintenance dose of peanut protein. Subjects who experience peanut-related hypotension as evidenced by a 15 % drop in their blood pressure from their baseline, nontransient oxygen desaturation below 90%, recurrent abdominal pain, or recurrent emesis which is felt by the PI to be potentially dose related will be stopped from participating in the study.

Any subject who has a serious adverse event which is felt by the PI to be potentially a result of participation in the study will be dropped from the study.

SAFETY MONITORING

This section defines the types of adverse events that should be reported. It outlines the procedures for the appropriate collection, grading, recording and reporting of the events.

Procedures and Monitoring

All unexpected serious adverse events related to the experimental procedures will be reported to the IRB, DCRU, DSMB, and FDA in a manner consistent with 21 CFR 312.32. All other adverse events related to the experimental procedures will also be reported to the IRB and DCRU in an expedited manner if they are Grade 3 and above in severity. Participant deaths are reportable within 24 hours. The expedited report sent to other organizations will be copied to the DCRU. The investigator will continue to follow or obtain documentation of the resolution course of such an event. A copy of the annual report of adverse events submitted to the IRB will be copied to the DCRU. Reactions to dosing of the study product will be recorded on a dosing log and will not be reported separately as adverse events. Any reaction that meets the criteria for a serious adverse event will be reported both on the dosing log and on an adverse event case report form.

Definitions

Adverse Event (AE) or Medical Event

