An adverse event is a new, undesirable medical event or occurrence or worsening of an existing condition (including an abnormal laboratory finding) in a subject that occurs during treatment and throughout the study, whether or not it is considered to be study related. Adverse events or medical events and toxicities are treatment emergent signs and symptoms.

Potential adverse reactions seen in subjects treated with peanut OIT and subjects undergoing DBPCFC include the following: skin manifestations such as pruritus, urticaria, or angioedema; respiratory symptoms such as wheezing, coughing, nasal congestion/rhinorrhea, cough and hoarseness; and gastrointestinal manifestations such as vomiting, diarrhea, or abdominal pain. Anaphylaxis is a potential risk involving any of the above symptoms plus hypotension and circulatory collapse.

Serious Adverse Event

A serious adverse event is defined as any adverse therapy experience occurring at any dose that results in the following (21 CFR 312.32):

1. Death: A death occurring during the study, or which comes to the attention of the investigator during the protocol-defined follow-up after the completion of therapy whether or not considered treatment related, must be reported.
2. Life-threatening: Any adverse therapy experience that places the subject or subjects, in the view of the investigator, at immediate risk of death from the reaction as it occurred (i.e., it does not include a reaction that, had it occurred in a more serious form, might have caused death).
3. In-patient hospitalizations or prolongation of existing hospitalization.
4. Persistent or significant disability or incapacity.

5. Congenital anomaly/birth defect.
6. An event that required intervention to prevent permanent impairment or damage.

Unexpected Adverse Event

An adverse event is considered “unexpected” when its nature (specificity) or severity is not consistent with applicable product information, such as safety information provided in the protocol or consent.

TOXICITY GRADING

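### A grade 3+ or epinephrine-treated dosing reaction not judged an SAE need not trigger the trial-level stopping rule, and neither document sends such reactions to the DSMB by arm

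*Protocol*

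**What the plan says.** **Trial-level rule.** Study Stopping Rules (Protocol) has two triggers: an FDA-defined SAE in any subject, or "an unanticipated event of grade 3 or above as defined by the CTC III scale, the trial will be halted". If symptoms described by a back-reference occur in two or more subjects, the study is stopped and reviewed. Epinephrine use is not mentioned.

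**What is known or unexpected.** The adverse event definition lists skin, respiratory and gastrointestinal reactions to peanut OIT and adds: "Anaphylaxis is a potential risk involving any of the above symptoms plus hypotension and circulatory collapse". An event is unexpected "when its nature (specificity) or severity is not consistent with applicable product information". SAE criterion 6 reads "An event that required intervention to prevent permanent impairment or damage".

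**Routing.** Procedures and Monitoring, under Safety Monitoring, says: "Reactions to dosing of the study product will be recorded on a dosing log and will not be reported separately as adverse events". Only reactions meeting SAE criteria also go on an adverse event form. The same paragraph says that other related adverse events are "reported to the IRB and DCRU in an expedited manner if they are Grade 3 and above in severity". The DSMB is named there for unexpected related SAEs. Recording and Reporting Procedures adds semi-annual DSMB monitoring without saying what the board receives.

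**Individual rules.** Children are taken off dosing for "moderate to severe clinical symptoms (GI, respiratory or skin) at home after taking the daily dose of peanut protein". An epinephrine-treated build-up reaction leads to at least four hours of observation.

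**SAP.** Randomization states that families, coordinators and investigators are blinded to dose. Sample size names a better safety profile as a possible advantage of low dose. Statistical Analysis contains no safety analysis.

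**The concern.** The rule sees the worst events. The gap lies one level below: reactions that needed epinephrine, or were graded 3 or higher, but were not called SAEs. Whether one of these pauses the trial depends on case-by-case judgement of an undefined word. The individual rules remove affected children one at a time and compare nothing across arms.

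The children are 9-36 months old at entry, and comparing a tenfold difference in maintenance dose is part of the purpose. An excess of such reactions in one arm is the signal that a monitoring board would want to see. Blinded staff cannot see it, and no unblinded body is assigned to look.

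**Working it through.** **1. Tracing one reaction through the text.** Take a home dosing reaction treated with epinephrine that resolves and is not judged an SAE.

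| Provision | Does it catch the reaction? |
|---|---|
| SAE trigger | No, by assumption. Criterion 6 could make it an SAE, but epinephrine is not named. |
| Unanticipated grade 3+ trigger | Open. Allergic reactions are listed risks, which points to anticipated. The severity part of *unexpected* points the other way, since the Protocol says "home dosing is safe, with infrequent reactions which are typically mild". Neither reading is prescribed. |
| Two-subject rule | If its back-reference reaches the preceding paragraph (respiratory failure, hypotension, ICU-level symptoms), two such cases stop the study, anticipated or not. Milder epinephrine-treated reactions are still missed. |
| Expedited reporting | Only at grade 3+, and only if the dosing-log sentence does not exempt it. Recipients are the IRB and DCRU. |
| Semi-annual DSMB review | Not stated either way. |

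Allergic reactions are graded on a modified scale in Appendix 2, which is not in the text available for review. The grade 3+ part of the point therefore cannot be sized. The epinephrine part can, roughly.

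**2. Inputs.**
- Pilot home rate (Preliminary Results, Table 2): r = 2/10,184 = 0.0196% per dose; exact 95% limits 0.0024% to 0.0709%.
- Treated children: 80 (Protocol) or 40 (SAP).
- Home days D, one dose a day. Table 3 has 20 build-up steps from 6 mg up to 3000 mg. Shortest course, with exit after 12 months of maintenance: 20 x 10 + 365 = 565. Longest, with 36 months taken as 1,092 days: 20 x 14 + 1,092 = 1,372.

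**3. Children with at least one epinephrine-treated home reaction**, n x (1 - exp(-rD)), doses taken as independent:
- r x 565 = 0.111, so 10.5% of children: 4.2 of 40, 8.4 of 80.
- r x 1,372 = 0.269, so 23.6%: 9.4 of 40, 18.9 of 80.
- Lower rate limit with 565 days, to upper rate limit with 1,372 days: 0.5 to 24.9 of 40; 1.1 to 49.8 of 80.

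If no child left dosing after a reaction, total reactions (n x D x r) would be 4.4-10.8 with 40 treated and 8.9-21.6 with 80.

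**4. Chance that none of these home reactions trips the SAE trigger.** With p from step 3 and an assumed share s judged SAEs, this is (1 - s x p)^n:

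| Assumed s | n = 40 | n = 80 |
|---|---|---|
| 10% | 38%-66% | 15%-43% |
| 50% | 0.7%-12% | at most 1.3% |

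**5. What a difference between arms would look like.** Assume 20 per arm, with one arm at the pilot rate and the other at three times that rate. On the evident reading of the masking text and Table 3, both arms take the same peanut dose through 245 mg, which is 10 of the 20 steps (100-140 days). The tripled rate is applied only after that.
- Lower arm: 20 x (1 - exp(-rD)) = 2.1 to 4.7 children.
- Higher arm, 565 days: r x (100 + 3 x 465) = r x 1,495 = 0.294, giving 5.1 children.
- Higher arm, 1,372 days: r x (140 + 3 x 1,232) = r x 3,836 = 0.753, giving 10.6 children.
- Blinded staff would see only the totals, 7.2 to 15.3.

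**The case against.** The strongest reply is that the plan is already strict. One SAE halts a trial of 40-80 children, and FDA approval is needed to resume. Keeping expected dosing reactions on their own log is a deliberate and common choice. The two sentences on routing can be reconciled if the log rule is read as avoiding duplicate case-report entries. The DSMB meets twice a year, is not on the SAP's list of blinded parties, and may well review the log; no charter is available to show otherwise. The size rests on two pilot events in older children (mean age 4.8 years).

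Much of this stands. A reader might infer that severe anaphylaxis cannot stop the trial. The documents do not support that: the SAE trigger, criterion 6, the severity wording and the two-subject rule can each reach severe cases. A reader might also infer that the DSMB is denied these data. The text is silent, which is not the same thing. Nor is the routing paragraph a flat contradiction; its two sentences sit awkwardly together.

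What remains is that the log sentence is a stated rule, not only an omission. Even if the expedited sentence prevails, it does not name the DSMB, and it leaves out epinephrine-treated reactions below grade 3. Nothing assigns a comparison by arm to anyone who could make it.

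**Conclusion.** The point holds in a limited form: as written, these reactions need not reach trial-level review, and no provision shows them by arm to an unblinded body. It is a low-cost improvement in oversight, not evidence that the trial is unsafe.

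The scale is about 4-9 of 40 or 8-19 of 80 children, with a range of roughly fiftyfold once the rate limits are included. This is no forecast. It assumes that the pilot rate carries over to younger children, that doses are independent, and that there is no dropout. Clustering within children would lower the number affected. So would the SAP's expected 15-20% dropout: if 20% contributed no doses at all, 4.2-9.4 of 40 would become 3.4-7.6.

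The SAE shares and the threefold ratio are illustrative. The no-trigger figures count home reactions only, and SAEs during the initial day, build-up visits or challenges could also halt the trial. The gap matters most if few of these reactions are judged SAEs, and the documents do not give that share.

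**What to change.** 1. Keep the any-SAE halt, and define *unanticipated* in Study Stopping Rules.
2. Amend Procedures and Monitoring so that every dosing reaction that is grade 3+ or treated with epinephrine is also recorded as an adverse event and included in the DSMB report.
3. Capture epinephrine use for home and build-up doses. The daily diary and the Dosage Escalation Sheet have no such field. The Desensitization/Challenge Sheet does, and the dosing log, which is not in the text available, may.
4. Have the existing unblinded staff give the DSMB closed cumulative counts at each semi-annual review: by arm above 245 mg, where peanut doses diverge, and pooled for the initial day and the shared build-up steps.
5. Add to the SAP a table of these reactions by arm per 1,000 doses.

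No numeric stopping limit is proposed, because the documents give no rate for this age group.

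Cost: one amendment, one medication field, one closed DSMB table and one SAP table. No extra patients or visits are needed, and keeping the by-arm counts in the closed report protects the blind.
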